8.2 TRIAL CLOSURE

9. STATISTICS AND DATA ANALYSIS

10. MONITORING

GLOSSARY OF ABBREVIATIONS

RCT	Randomised Controlled Trial
GDM	Gestational Diabetes Mellitus

POST-GDM-DNA; Post-delivery intervention for weight loss, glycaemia and cardiovascular health

IRAS ID 292085

Protocol v12.1 8/3/22

CI	Chief investigator
TMG	Trial Management Group
GCP	Good clinical practice
HbA1c	Glycated haemoglobin - monitors average blood glucose
HDL	High-density lipoprotein cholesterol
LDL	Low-density lipoprotein cholesterol
BP	Blood pressure

KEYWORDS

Weight, blood pressure, glycaemia, HbA1c, physical activity, wearable, postnatal, post-delivery, DNA, personalised

STUDY SUMMARY

TITLE Post-delivery intervention in women with previous gestational diabetes mellitus for weight loss, glycaemia and cardiovascular health

DESIGN Feasibility study

Allocation: RCT

AIMS To determine the feasibility of a post-delivery intervention to improve glycemia and cardiovascular function and promote weight loss in women who have had gestational diabetes.

OUTCOME MEASURES Primary outcome; Effect of intervention on HbA1c: difference in HbA1c between intervention arm and control arm measured at 12 weeks.

Secondary Outcomes;

- Adherence to intervention;
- Willingness to be randomised to post-delivery intervention;
- Process measures to evaluate patient experience of study and intervention;
- Participants' preferred time to commence the study, within the start date allowance of 6 weeks – 6 month post-delivery.
- Between-arm differences and within-arm differences to evaluate:
 - Effect of intervention on HbA1c at 12 and 24 weeks
 - Effect of intervention on weight and BMI at 12 and 24 weeks
 - Effect of intervention on systolic and diastolic blood pressure at 12 and 24 weeks
 - Effect of intervention on lipid profile (total cholesterol, HDL, LDL) at 12 and 24 weeks
 - Effect of intervention on physical activity at 12 and 24 weeks

POPULATION We will recruit 50 women aged 18-45 with previous gestational diabetes and randomise them to 1 of 2 arms to commence study at 6 weeks – 6 months post-delivery. Women starting the study at 13 weeks post-delivery will have their routine post-delivery HbA1c act as baseline HBA1c.

ELIGIBILITY Pregnant women with gestational diabetes (women will be given the option to start the study between 6 weeks and 6 months post-delivery) or women who have given birth in the last 12 months and had gestational diabetes during that pregnancy; aged 18-45; and access to a smartphone with an operating system of iOS 9.0 or above, or Android 5.0 or above.

DURATION Study duration: 1/4/21-1/9/22. Participant duration: 24 weeks

[figure not shown]

Figure 1: Study design. *Intervention starts at week 1 and coincides with routine NHS postnatal check on blood glucose = baseline blood glucose (at 13 weeks post-delivery).

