3. STUDY DESIGN

We will conduct a feasibility study for an open-label, randomised, controlled trial of a personalised post-delivery intervention (*DNA Nudge*) to improve weight, glycaemia and cardiovascular function in women with previous GDM.

The study is designed to be remote, to enable the study to begin and continue in the pandemic and minimise barriers to recruitment. Study participants will be provided with equipment and instructions to collect samples and measurements at home. Contact with the research team will be over telephone or Microsoft Teams video call.

We will advertise in diabetes antenatal clinics using word-of-mouth, posters, social media and on departmental emails at Imperial College Healthcare NHS Trust or Imperial College POST-GDM-DNA; Post-delivery intervention for weight loss, glycaemia and cardiovascular health IRAS ID 292085

for women with current/previous GDM aged 18-45. We will recruit via Twitter, email and in-person encounters.

We will randomise women to 1 of 2 arms:

Arm 1: Standard dietary and physical activity advice as per NICE guidelines at week 1 (active control arm; n = 25)

Arm 2: DNA-based personalised dietary and physical advice delivered by DNA Nudge dietician at week 1 and by DNA Nudge wearable and app for weeks 1-24 (intervention arm; n = 25)

Women not randomised to DNA Nudge will be provided with an activity app/wearable device (Fitbit) to monitor daily step count. All women will be provided with a home BP monitor and weighing scales.

Week 1

Eligibility assessment, consent, randomisation, IPAQ questionnaire, baseline BP and weight, blood sample collected for baseline lipid profile.

Some women will begin the study at 13 weeks post-delivery and coincide with the routine postnatal HbA1c for women with GDM. The routine post-delivery HbA1c will be baseline HbA1c for this study. For women who commence the study outside the 13 weeks post-delivery window, a finger prick blood sample will be used for a baseline HbA1c test.

Women in the control arm will be given standard dietary and physical activity advice by the research team, in line with NICE guidelines.

Women in the DNA Nudge arm will provide a cheek swab for DNA analysis, carried out by DNA Nudge. They will be given personalised dietary advice by a DNA Nudge dietician, and be provided with DNA Nudge wearable, app and instructions.

Week 6:

Telephone/video-call follow-up to check ongoing willingness to participate and assess adherence.

Week 12:

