4. PARTICIPANT ENTRY

4.1 PRE-RANDOMISATION EVALUATIONS Women replying to our adverts will be assessed for eligibility by questionnaire.

4.2 INCLUSION CRITERIA Pregnant women with gestational diabetes (women will be given the option to start the study between 6 weeks and 6 months post-delivery) or women who have given birth in the last 12 months and had gestational diabetes during that pregnancy, aged 18-45, access to a smartphone with an operating system of iOS 9.0 or above, or Android 5.0 or above [CB: operating systems correct as of 23/03/21]

4.3 EXCLUSION CRITERIA Diabetes outside of pregnancy (diagnosis of type 1 or 2 diabetes; or HbA1c 48 mmol/mol or above). Health contra-indications to moderate-vigorous exercise. Planning pregnancy during the study period or become pregnant during the study period. Cancer, kidney disease, liver disease, or pancreatitis. Have had gastric bypass surgery or similar weight loss surgery.

4.4 WITHDRAWAL CRITERIA If women withdraw consent or become pregnant during the study period, the data collected to that point will be retained, they will be withdrawn from the study and we will request permission to collect safety outcomes from them.

If they agree to participate, consent will be gained and stored in the site file.

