5. RANDOMISATION AND ENROLMENT PROCEDURE

This will be an open-label trial. Randomisation will be in a 1:1 ratio by serially numbered, sealed, opaque envelopes, which will be prepared by a member of staff outside the research team.

Randomisation will be stratified by breastfeeding status (yes/no) at the time of recruitment.

5.1 RANDOMISATION OR REGISTRATION PRACTICALITIES Sealed envelopes will kept in a locked filing cabinet in a research office at Queen Charlotte's and Chelsea Hospital. Randomisation will occur in person at the QCCH site.

5.2 UNBLINDING This will be an open-label study. Data analysis will be study-arm blinded, unblinding will occur after completion.

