8. STATISTICS AND DATA ANALYSIS

A study master list with patient identifiable information will be stored on a password-protected NHS computer in a locked research office at Queen Charlotte's and Chelsea Hospital, accessible only to the research team. This will match patient identifiable information with their study identification number. This study identification number will be used for the study database, which will be a cloud-based Excel database, which will be password protected and accessible only by the research team.

If any health conditions are discovered incidentally during the study they would be discussed with the participant immediately and their consent sought to share the information with their GP for the arrangement of their ongoing healthcare.

The study sample is 50 participants, 25 in each arm. The sample size has been based on guidance from the NIHR on pilot/feasibility studies (12) and the literature that it references that concludes that pilot studies should look for a sample size of at least 50 (13).

Data will be analysed after all participants have completed the 24 study weeks and all data is collected. Patient demographics will be presented as median/range or as categorical data where appropriate. We will evaluate primary and secondary outcomes using descriptive statistics. Between group comparison will be made using logistic regression.

Data and all appropriate documentation will be stored for 10 years after the completion of the study in accordance with ICHT guidance.

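### Within-arm change cannot show an intervention effect, and the between-arm analysis names no adjustment for baseline value, stratum or weeks since delivery

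*Combined protocol and SAP*

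**What the plan says.** - **Start time.** The Study Summary and section 2 make the preferred start an outcome, "within the start date allowance of 6 weeks – 6 month post-delivery". The population paragraph of the Study Summary says the study will recruit 50 women and "randomise them to 1 of 2 arms to commence study at 6 weeks – 6 months post-delivery". Section 3 shows that the start is not fixed: "Some women will begin the study at 13 weeks post-delivery and coincide with the routine postnatal HbA1c for women with GDM". Section 4.2 also admits "women who have given birth in the last 12 months and had gestational diabetes during that pregnancy", which does not match a six-month limit.
- **Allocation.** Section 5: "Randomisation will be in a 1:1 ratio by serially numbered, sealed, opaque envelopes". The only stratum is breastfeeding: "Randomisation will be stratified by breastfeeding status (yes/no) at the time of recruitment".
- **Outcomes.** The primary outcome is the difference between arms in HbA1c at 12 weeks. The clinical secondary outcomes are introduced by "Between-arm differences and within-arm differences to evaluate", followed by HbA1c, weight and BMI, blood pressure, lipids and activity at 12 and 24 weeks, each worded as an intervention effect.
- **Analysis.** The statistics section (headed 8, listed as 9 in the contents) plans descriptive statistics and then one model: "Between group comparison will be made using logistic regression". It names no covariate and no cut-point that would make a continuous outcome binary.

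**The concern.** There are two separate issues.

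First, the Study Summary gives within-arm change the same standing as the randomised contrast. Women are measured over 24 weeks that begin soon after a pregnancy. Any change over that time, whatever its cause, appears in full in each arm's before-and-after difference. If the intervention arm's change is reported as the effect of the intervention, the report makes a claim that the design cannot support.

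Second, women enter at very different times after delivery, and the analysis makes no use of this. Breastfeeding status does not stand in for it, because it is recorded at recruitment, when some women may still be pregnant. The baseline value and the stratum used in allocation are also left out, and the named model does not give a mean difference for a continuous outcome. At stake is some precision, and an arm difference that has not been adjusted for known characteristics that happen to be uneven in a trial of 25 per arm.

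**Working it through.** The plan has no figure of its own to reproduce here. The sample size is 25 + 25 = 50, taken from pilot-study guidance, and no standard deviation, effect size or error rate is given.

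**1. What within-arm change measures.** Let N be the mean change over time that would occur anyway, P the effect of the personalised advice and S the effect of the standard advice.
- Change in arm 2 = N + P
- Change in arm 1 = N + S
- Difference between arms = P − S

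N cancels only in the last line. Start time does not enter the argument: N would remain in each arm's change if every woman began at 13 weeks. Arm 1 also receives advice, so its change is not pure natural history either.

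**2. Spread of start time.** One month = 365.25 / 12 / 7 = 4.348 weeks, so 6 months = 26.1 weeks and 26.1 / 6 = 4.35. The week-12 visit falls 6 + 12 = 18 to 26.1 + 12 = 38.1 weeks after delivery. One woman's baseline can therefore be later after delivery than another's week-12 visit.

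**3. Chance imbalance between arms (25 per arm).** Assume starts uniform over 6 to 26 weeks.
- SD of start time = 20 / √12 = 5.77 weeks
- SE of the arm difference in means = 5.77 × √(2/25) = 1.63 weeks
- 95% range = ±1.96 × 1.63 = ±3.2 weeks; a gap of more than 2 weeks has probability about 22%

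Now assume instead that half start at exactly 13 weeks and the rest are uniform. The mean is 14.5 and the variance is ½(1.5²) + ½(33.3 + 1.5²) = 18.9, so the SD is 4.35, the SE 1.23 and the range ±2.4 weeks.

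**4. The same imbalance in outcome units.** 3.2 / 5.77 = 0.55 SD of start time. If weeks since delivery explained 5% to 15% of outcome variance (assumption; r = 0.22 to 0.39), the shift would be 0.55 × 0.22 = 0.12 to 0.55 × 0.39 = 0.21 SD of the outcome. The unadjusted 95% half-width is already 1.96 × √(2/25) = 0.55 SD.

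**5. Gain and cost of the extra covariate.** Let q be the share of outcome variance that weeks since delivery explains after arm, baseline value and stratum. The interval narrows by the factor √(1 − q).

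| q (assumed) | factor | narrower by |
|---|---|---|
| 0 | 1.000 | 0% |
| 0.05 | 0.975 | 2.5% |
| 0.15 | 0.922 | 7.8% |

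The documents give no value for q. The baseline value may already carry most of what start time explains, so q may be near zero. The model has five coefficients (intercept, arm, baseline, stratum, weeks), which leaves 50 − 5 = 45 residual degrees of freedom, against 46 without weeks. A useless covariate widens the interval by roughly √(46/45) = 1.011, or about 1%.

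**The case against.** The strongest reply is that allocation is randomised and the primary outcome is a between-arm difference, so change after delivery affects both arms and cancels in expectation. That stands. A reader might infer that, because start time varies and is unadjusted, postnatal change is mixed into the trial's effect estimate. The documents do not support this for the between-arm contrast. Chance imbalance is ordinary sampling error, which an unadjusted interval already allows for (step 4). Nor is the varying start what makes within-arm change uninterpretable (step 1), and adjusting for weeks since delivery would not cure that.

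It can also be said that the plan contains no within-arm test, only description and one between-group comparison. That stands too. With 25 women, no intervention effect and an assumed natural shift of 0.2 to 0.8 SD of change, a within-arm t-test at 5% two-sided would be significant in 16% to 97% of trials, but those rates belong to a test that the plan does not include. The fault is that the Study Summary presents uncontrolled change as a way to evaluate effect and nothing later restricts it to description.

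A wider imbalance, about ±7.4 weeks, follows only if starts run uniformly to 52 weeks. That rests on the 12-month eligibility wording, which conflicts with the six-month start limit. The two need reconciling as a separate matter, and the larger figure should not be used here.

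Finally, this is a 50-woman feasibility study and the value of the covariate is unproven. That limits the weight of the point. It does not remove it, because the primary outcome is itself an effect on HbA1c and the remedy costs little.

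**Conclusion.** The point holds as a modest, inexpensive improvement. Two things are certain from the text: within-arm change is listed as a way to evaluate effect although it has no comparator, and the statistics section names neither a suitable model for continuous outcomes nor any covariate. The between-arm estimates are not biased by the spread of start times.

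The size of the second issue depends on assumptions. The imbalance in mean start time is about ±3.2 weeks with uniform starts over 6 to 26 weeks, and about ±2.4 weeks if half start at 13 weeks. Adjusting for weeks since delivery would narrow intervals by 0% to about 8% for q between 0 and 0.15, and the true q is unknown. The size of any natural change after delivery is also not given, so the bias in within-arm change cannot be quantified, but within-arm change does not identify the effect at any size.

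**What to change.** In the statistics section, replace the logistic regression sentence, for continuous outcomes, with a linear model at 12 and at 24 weeks containing arm, baseline value, breastfeeding stratum and weeks since delivery at start (continuous). Report the adjusted between-arm difference with its 95% confidence interval.

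In the Study Summary, state that within-arm changes are descriptive only and that every statement about the effect of the intervention rests on the adjusted between-arm difference.

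The cost is wording and a few degrees of freedom, with about 45 left if all 50 women contribute. Section 3 already collects baseline HbA1c, weight, blood pressure, lipids and IPAQ, and the delivery date is needed to apply the start window. For activity, section 3 lists the IPAQ at weeks 1 and 24 but not at week 12, so the plan should say which measure serves at 12 weeks. If weeks since delivery adds nothing beyond baseline, the loss is about 1% in interval width.

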1. INTRODUCTION

1.1 BACKGROUND

In the UK, 60% of women and 28% of children are overweight or obese, children's overweight and obesity is associated with that of their parents (1). Overweight and obesity are associated with cardiovascular disease, diabetes and cancer, the leading causes of death (prior to the COVID-19 pandemic) for women in the UK and are associated with increased risk of death from the COVID-19 pandemic (2). Overweight and obesity are also associated with nearly all major pregnancy complications, including pre-term birth, stillbirth, gestational hypertension, pre-eclampsia, gestational diabetes and maternal death (3). Pre-conception BMI is also associated with offspring BMI.

Gestational diabetes (GDM) affects 2-18% of pregnancies and is associated with stillbirth, pre-term delivery, macrosomia, birth trauma, neonatal hypoglycaemia and offspring overweight and obesity(4). Women with GDM have 10 times the risk of those not affected by GDM of developing type-2 diabetes in the 10 years after delivery(5). As such, the post-delivery period represents a unique point for secondary prevention – of recurrent GDM- and primary preventions of type-2 diabetes in a high-risk group.

GDM often co-exists with other pregnancy complications, including hypertension in pregnancy.

No major study has yet examined the use of a post-delivery or inter-conception personalised dietary and exercise intervention using DNA-based dietary advice.

Personalised nutrition enables health interventions by optimising multiple dietary components simultaneously and enhancing motivation to adhere to dietary advice. An innovative approach to personalised nutrition has emerged in the form of DNA-based dietary advice. This intervention provides people with dietary advice that has been tailored to information based on their DNA.

In a study in which a DNA-based diet was used to treat obesity in participants with ≥ 2 unsuccessful attempts to lose weight, a personalised, DNA-based diet saw 19/26 (73%) participants maintain weight loss at 300 days compared with 7/22 (32%) of participants who were given standard Mediterranean dietary advice. Additionally, it also had a dramatic effect on the fasting blood glucose levels of participants (10). Notably, the DNA-based nutritional advice was not tailored to be a weight loss program. It was targeted to optimise the nutrient profile of a given individual. Another point of interest was the longevity of the effect. The greatest difference between the intervention and control group was found >300 days post treatment; the control cohort showed a slight increase in BMI, compared to the decrease found in the intervention group.

This may indicate that there is a greater probability of long-term adherence to nutritional guidelines when tailored, actionable DNA-based advice is provided. A prospective study examined the potential for DNA-based advice to enhance adherence to nutrition protocols (11). Participants received general dietary advice, versus the same advice supplemented with information based on their DNA (n = 149). Those in the intervention group reported a greater understanding of the dietary advice (93% versus 78%), they were more likely view the advice as useful (88% versus 72%), and they were more interested in receiving further recommendations (95% versus 76%).

1.2 RATIONALE FOR CURRENT STUDY

General advice for women with previous GDM planning pregnancy exists on the NHS website, which describes the benefits of taking folic acid, smoking and alcohol cessation, keeping to a healthy weight, vaccinations and management of long-term conditions. No specific intervention is recommended for this group of women.

Consulting our Pre-conception PPI group, funded by an Imperial NIHR BRC PPI grant, we have found that women tend to use a variety of pregnancy planning or pre-conception information, the majority of which is obtained from internet searches, social media and their peers. Women planning pregnancy reported they would be willing to engage in a pre-pregnancy intervention using ‘natural’ interventions rather than medication, small changes to their daily routine dietary advice which do not focus on weight loss *per-se* but rather a personalised approach to nutrition.

Our group has previously conducted a cohort study recruiting women planning pregnancy, recruitment of 530 women who had 356 pregnancies and 218 deliveries at Queen Charlotte’s hospital (9).

We propose to evaluate the feasibility of a post-delivery intervention in women who have had GDM using a novel wearable device which uses focussed genetic analysis of the wearer to allow personalised decisions on food and lifestyle improvement to be made by the wearer. We will also evaluate its effect on participants’ weight, physical activity and cardiovascular function.

2. STUDY OBJECTIVES

Objectives

To assess:

1. Effect of intervention on HbA1c at 12 and 24 weeks
2. Adherence to intervention
3. Participants’ preferred time to commence the study, within the start date allowance of 6 weeks – 6 month post-delivery.
4. Qualitative data on how participants found post-delivery intervention
5. Effect of intervention on weight at 12 and 24 weeks
6. Effect of intervention on systolic and diastolic blood pressure at 12 and 24 weeks
7. Effect of intervention on lipid profile (total cholesterol, HDL, LDL) at 12 and 24 weeks
8. Effect of intervention on physical activity at 12 and 24 weeks

3. STUDY DESIGN

We will conduct a feasibility study for an open-label, randomised, controlled trial of a personalised post-delivery intervention (*DNA Nudge*) to improve weight, glycaemia and cardiovascular function in women with previous GDM.

The study is designed to be remote, to enable the study to begin and continue in the pandemic and minimise barriers to recruitment. Study participants will be provided with equipment and instructions to collect samples and measurements at home. Contact with the research team will be over telephone or Microsoft Teams video call.

We will advertise in diabetes antenatal clinics using word-of-mouth, posters, social media and on departmental emails at Imperial College Healthcare NHS Trust or Imperial College POST-GDM-DNA; Post-delivery intervention for weight loss, glycaemia and cardiovascular health IRAS ID 292085

for women with current/previous GDM aged 18-45. We will recruit via Twitter, email and in-person encounters.

We will randomise women to 1 of 2 arms:

Arm 1: Standard dietary and physical activity advice as per NICE guidelines at week 1 (active control arm; n = 25)

Arm 2: DNA-based personalised dietary and physical advice delivered by DNA Nudge dietician at week 1 and by DNA Nudge wearable and app for weeks 1-24 (intervention arm; n = 25)

Women not randomised to DNA Nudge will be provided with an activity app/wearable device (Fitbit) to monitor daily step count. All women will be provided with a home BP monitor and weighing scales.

Week 1

Eligibility assessment, consent, randomisation, IPAQ questionnaire, baseline BP and weight, blood sample collected for baseline lipid profile.

Some women will begin the study at 13 weeks post-delivery and coincide with the routine postnatal HbA1c for women with GDM. The routine post-delivery HbA1c will be baseline HbA1c for this study. For women who commence the study outside the 13 weeks post-delivery window, a finger prick blood sample will be used for a baseline HbA1c test.

Women in the control arm will be given standard dietary and physical activity advice by the research team, in line with NICE guidelines.

Women in the DNA Nudge arm will provide a cheek swab for DNA analysis, carried out by DNA Nudge. They will be given personalised dietary advice by a DNA Nudge dietician, and be provided with DNA Nudge wearable, app and instructions.

Week 6:

Telephone/video-call follow-up to check ongoing willingness to participate and assess adherence.

Week 12:

Collect weight and BP data from weeks 1-12, collect blood sample for HbA1c and lipid profile. Check ongoing willingness to participate and assess adherence.

Week 18:

Telephone/video-call follow-up to check ongoing willingness to participate and assess adherence.

Week 24:

Collect weight and BP data from weeks 12-24, follow-up IPAQ questionnaire, collect blood sample for HbA1c and lipid profile, return devices and collect usage data from DNA Nudge. Qualitative questionnaire to explore intervention experience.

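### For women who start at 13 weeks post-delivery, baseline HbA1c is a routine NHS test and follow-up is a study sample, so within-arm HbA1c change may mix a change of test with real change

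*Combined protocol and SAP*

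**What the plan says.** The Study Summary (Population) states: "Women starting the study at 13 weeks post-delivery will have their routine post-delivery HbA1c act as baseline HBA1c". The Week 1 entry in section 3 (Study Design) repeats the rule: "The routine post-delivery HbA1c will be baseline HbA1c for this study". For women who start outside that window, "a finger prick blood sample will be used for a baseline HbA1c test". The 13-week start is described as coinciding with the routine check, but the width of the window is not given. The Figure 1 legend describes the routine check as one of blood glucose rather than HbA1c.

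The Week 1 entry also lists "baseline BP and weight, blood sample collected for baseline lipid profile", with no restriction by start time. At week 12 the plan is "Collect weight and BP data from weeks 1-12, collect blood sample for HbA1c and lipid profile", and at week 24 "follow-up IPAQ questionnaire, collect blood sample for HbA1c and lipid profile". On setting, section 3 says: "Study participants will be provided with equipment and instructions to collect samples and measurements at home".

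The primary outcome in the Study Summary is the between-arm difference in HbA1c at 12 weeks. The secondary outcomes include between-arm and within-arm differences in HbA1c at 12 and 24 weeks. The Statistics and Data Analysis section plans descriptive statistics and logistic regression. It names no baseline covariate and does not say how two baseline sources will be handled. Randomisation (section 5) is stratified by breastfeeding status only.

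**The concern.** A within-arm change is follow-up minus baseline, and it can be read as change in the woman only if both values come from comparable tests. For 13-week starters the baseline is a routine NHS result and the follow-up is a study sample. Any systematic difference between the two in specimen, laboratory or assay goes straight into their change scores. If the routine test reads higher, HbA1c appears to fall in both arms; if it reads lower, a real fall is hidden.

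Which source a woman has depends on when she starts, so source is also tied to time since delivery. No method comparison is planned, and the plan does not ask for source to be recorded as a variable. A modest within-arm fall in HbA1c, which could be cited in support of a larger trial, might then be partly or wholly a change of test.

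**Working it through.** The sample size has no power calculation behind it, so there is no HbA1c figure in the plan to reproduce. The only check available, 25 + 25 = 50, agrees. The rest is a comparison of sources and an illustration with assumed inputs.

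**Sources compared**

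- 13-week starters: routine NHS test at baseline, study sample at weeks 12 and 24. The source changes.
- All other starters: study finger-prick at baseline, study sample at weeks 12 and 24. If follow-up is also a home finger-prick, as the remote design suggests, the source does not change. The follow-up specimen type is not stated.

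**Inputs**

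- n = 25 per arm (Statistics and Data Analysis section).
- f, the share of women who start at 13 weeks: assumed 0.3 to 0.7. The plan says only that some women will.
- b, the offset between routine and study test: assumed 1 to 3 mmol/mol. No figure is given.
- SD of HbA1c: assumed 3 to 5 mmol/mol. Baseline-outcome correlation r: assumed 0.7.

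**Step 1. Bias in mean within-arm change**

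Size of bias = f × b.

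- Low end: 0.3 × 1 = 0.3 mmol/mol.
- Middle: 0.5 × 2 = 1.0 mmol/mol.
- High end: 0.7 × 3 = 2.1 mmol/mol.

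For scale, the 95% half-width for mean change in one arm is about 1.96 × SD × √(2(1 − r)) / √25, with equal SDs at both times and complete follow-up. SD 3 gives 1.96 × 3 × 0.775 / 5 = 0.9; SD 5 gives 1.96 × 5 × 0.775 / 5 = 1.5 mmol/mol. The bias runs from well below this uncertainty to above it.

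**Step 2. Between-arm difference in change, if reported**

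Both arms follow the same source rule, so the expected bias is 0. Chance imbalance in source has SD b × √(2f(1 − f)/25):

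- b = 1, f = 0.3: √(0.42/25) = 0.13 mmol/mol.
- b = 3, f = 0.5: 3 × √(0.50/25) = 0.42 mmol/mol.

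**Step 3. Primary outcome**

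The week-12 contrast compares study samples with study samples and has no baseline term. The bias from baseline source is 0, and the planned analysis loses no precision from it. The half-width of that contrast is 1.96 × SD × √(2/25), or 1.7 to 2.8 mmol/mol for SD 3 to 5, whatever the baseline source.

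**Step 4. If a baseline-adjusted analysis were added**

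An offset b in a share f adds f(1 − f)b² to the baseline variance. Then r² becomes 0.49 × SD² / (SD² + f(1 − f)b²), and CI width is multiplied by √((1 − new r²)/0.51).

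- b = 1, f = 0.3, SD 5: r² = 0.49 × 25/25.21 = 0.486; √(0.514/0.51) = 1.004, about 0.4% wider.
- b = 2, f = 0.5, SD 4: r² = 0.49 × 16/17 = 0.461; √(0.539/0.51) = 1.028, about 3% wider.
- b = 3, f = 0.5, SD 3: r² = 0.49 × 9/11.25 = 0.392; √(0.608/0.51) = 1.092, about 9% wider.

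Because f(1 − f) is symmetric about 0.5, shares of 50-70% give the same range as 30-50%.

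**The case against.** The strongest reply is that this is a disclosed choice, applied equally to both arms, in a 50-woman feasibility study whose remote design is meant to keep the burden low. No assay, laboratory or specimen type is given for the routine or follow-up tests, so an offset is possible but not demonstrated, and the bias figures are the product of two assumed inputs. The plan also aligns the 13-week start with the routine test, so there is little ground for complaint about its date. All of this stands. It makes the bias conditional and keeps the point modest. It does not answer the fact that a listed outcome depends on comparability that the plan neither establishes nor checks.

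Three stronger readings are tempting and should be resisted.

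- A reader might infer that the primary comparison is biased or weakened. It is neither: its definition has no baseline term and the analysis section plans no baseline covariate.
- A reader might suppose a large loss of precision under adjustment, for example r falling from 0.7 to 0.6, which would widen the CI by √(0.64/0.51) − 1 = 12%. Offsets of 1-3 mmol/mol do not produce this at SDs of 3-5. It would need an SD near 2.5 with b = 3 and f = 0.5, or extra random error for which there is no evidence. A source indicator would also absorb a constant offset for one degree of freedom.
- A reader might infer that no woman's baseline matches her follow-up. The text shows a change of source only for 13-week starters.

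One practical caution also stands. The week-1 blood sample is listed for lipids only, and nothing confirms that it suits HbA1c as well. That one sample serves both tests at weeks 12 and 24 makes it likely.

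**Conclusion.** The point holds as a limited, conditional one. The change of test source for 13-week starters is plain in the text; whether the two tests differ systematically is not known from the documents. If they do, mean within-arm HbA1c change is biased by 0.3 to 2.1 mmol/mol under the assumed shares and offsets, and the plan has no means of detecting or removing this. The expected effect on any between-arm difference in change is zero, and the primary week-12 difference is untouched. A precision cost arises only if baseline adjustment is added, and is then about 0.4-9% in CI width under the stated assumptions. This is a worthwhile, inexpensive improvement to a secondary outcome and no threat to the main comparison.

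**What to change.** Measure HbA1c in every woman at week 1 from the study blood sample already listed for lipids, with the same collection method and laboratory as weeks 12 and 24. Confirm first that the sample suits both tests. Use this value as the baseline for change, keep the routine NHS result as descriptive data, and state the specimen type and laboratory for all three time points.

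Where that is not possible, including for any woman already enrolled without a week-1 study HbA1c, record the baseline source and report within-arm change separately by source or adjust for it. Define the width of the 13-week window, and reconcile the Figure 1 legend (blood glucose) with the Study Summary and section 3 (HbA1c).

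The cost is one extra HbA1c assay per 13-week starter, at most 50, with no extra visit. The fallback costs one recorded variable and a small extra table.
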